### **11.1 Protocol amendments**

Any change or addition to the protocol can only be made in a written protocol amendment that must be approved by Novartis, health authorities where required, and the IRB/IEC prior to implementation. Only amendments that are intended to eliminate an apparent immediate hazard to patients may be implemented immediately provided the health authorities are subsequently notified by protocol amendment and the reviewing IRB/IEC is notified. Notwithstanding the need for approval of formal protocol amendments, the investigator is expected to take any immediate action required for the safety of any patient included in this study, even if this action represents a deviation from the protocol. In such cases, the reporting requirements identified in Section 7 (Safety monitoring) must be followed.

## 13 Appendices

### 13.1 Appendix 1: Clinically notable laboratory values

The following criteria included in [Table 13-1](#) will be used to define expanded limits and notable abnormalities of key laboratory tests.

Clinically notable values will be forwarded to Novartis at the same time that they are sent to investigators. Any action based on these laboratory values should be discussed with Novartis personnel.

**Table 13-1 Safety analyses: expanded limits and notable criteria**

Laboratory variable	Final harmonization	
	Standard units	SI units
Liver function and related variables		
AST/SGOT	> 3 x ULN	> 3 x ULN
ALT/SGPT	> 3 x ULN	> 3 x ULN
Bilirubin	> 2 x ULN	> 2 x ULN
Alkaline phosphatase	> 2.5 x ULN	> 2.5 x ULN
Renal function and related variables		
Creatinine (serum)	> 2 x ULN	> 2 x ULN
Hematology variables		
Hemoglobin	20 g/L decrease from Baseline	
Platelet count	< 100 x 10E  /L	
White blood cell count	< 0.8 x LLN	
Neutrophils	< 0.9 x LLN	

ALT/SGPT=alanine aminotransferase/serum glutamic pyruvic transaminase, AST/SGOT=aspartate aminotransferase/serum glutamic oxaloacetic transaminase, LLN=lower limit of normal, ULN=upper limit of normal

## 13.2 Appendix 2: Liver event and laboratory trigger definitions and follow-up requirements

**Table 13-2 Liver event and laboratory trigger definitions**

	Definition/ threshold
Liver laboratory triggers	
 
• <math>3 \times \text{ULN} < \text{ALT} / \text{AST} \leq 5 \times \text{ULN}</math>
 
• <math>1.5 \times \text{ULN} < \text{TBL} \leq 2 \times \text{ULN}</math>
 

Liver events	
 
• <math>\text{ALT}</math> or <math>\text{AST} > 5 \times \text{ULN}</math>
 
• <math>\text{ALP} > 2 \times \text{ULN}</math> (in the absence of known bone pathology)
 
• <math>\text{TBL} > 2 \times \text{ULN}</math> (in the absence of known Gilbert syndrome)
 
• <math>\text{ALT}</math> or <math>\text{AST} > 3 \times \text{ULN}</math> and <math>\text{INR} > 1.5</math>
 
• Potential Hy's Law cases (defined as <math>\text{ALT}</math> or <math>\text{AST} > 3 \times \text{ULN}</math> and <math>\text{TBL} > 2 \times \text{ULN}</math> [mainly conjugated fraction] without notable increase in <math>\text{ALP}</math> to <math>> 2 \times \text{ULN}</math>)
 
• Any clinical event of jaundice (or equivalent term)
 
• <math>\text{ALT}</math> or <math>\text{AST} > 3 \times \text{ULN}</math> accompanied by (general) malaise, fatigue, abdominal pain, nausea, or vomiting, or rash with eosinophilia
 
• Any adverse event potentially indicative of a liver toxicity*
 

\*These events cover the following: hepatic failure, fibrosis and cirrhosis, and other liver damage-related conditions; the non-infectious hepatitis; the benign, malignant and unspecified liver neoplasms  
 $\text{ALT}$ =alanine aminotransferase,  $\text{ALP}$ =alkaline phosphatase,  $\text{AST}$ =aspartate aminotransferase,  $\text{INR}$ =international normalized ratio,  $\text{TBL}$ =total bilirubin,  $\text{ULN}$ =upper normal limit

**Table 13-3 Follow-up requirements for liver events and laboratory triggers**

Criteria	Actions required	Follow-up monitoring
Potential Hy's Law case a	
 
• Discontinue the study treatment immediately
 
• Hospitalize, if clinically appropriate
 
• Establish causality
 
• Complete liver CRF
 
	$\text{ALT}$ , $\text{AST}$ , $\text{TBL}$ , $\text{Alb}$ , $\text{PT/INR}$ , $\text{ALP}$ and $\gamma\text{GT}$ until resolution c (frequency at investigator discretion)
ALT or AST		
$> 8 \times \text{ULN}$	
 
• Discontinue the study treatment immediately
 
• Hospitalize if clinically appropriate
 
• Establish causality
 
• Complete liver CRF
 
	$\text{ALT}$ , $\text{AST}$ , $\text{TBL}$ , $\text{Alb}$ , $\text{PT/INR}$ , $\text{ALP}$ and $\gamma\text{GT}$ until resolution c (frequency at investigator discretion)
$> 3 \times \text{ULN}$ and $\text{INR} > 1.5$	
 
• Discontinue the study treatment immediately
 
• Hospitalize, if clinically appropriate
 
• Establish causality
 
• Complete liver CRF
 
	$\text{ALT}$ , $\text{AST}$ , $\text{TBL}$ , $\text{Alb}$ , $\text{PT/INR}$ , $\text{ALP}$ and $\gamma\text{GT}$ until resolution c (frequency at investigator discretion)
$> 5$ to $\leq 8 \times \text{ULN}$	
 
• Repeat LFT within 48 hours
 
• If elevation persists, continue follow-up monitoring
 
	$\text{ALT}$ , $\text{AST}$ , $\text{TBL}$ , $\text{Alb}$ , $\text{PT/INR}$ , $\text{ALP}$ and $\gamma\text{GT}$ until resolution c (frequency at investigator discretion)

Criteria	Actions required	Follow-up monitoring
	
 
If elevation persists for more than 2 weeks, discontinue the study drug
 
Establish causality
 
Complete liver CRF
 
	
> 3 × ULN accompanied by symptoms b	
 
Discontinue the study treatment immediately
 
Hospitalize if clinically appropriate
 
Establish causality
 
Complete liver CRF
 
	ALT, AST, TBL, Alb, PT/INR, ALP and γGT until resolution c (frequency at investigator discretion)
> 3 to ≤ 5 × ULN (patient is asymptomatic)	
 
Repeat LFT within the next week
 
If elevation is confirmed, initiate close observation of the patient
 
	Investigator discretion Monitor LFT within 1 to 4 weeks
ALP (isolated)		
> 2 × ULN (in the absence of known bone pathology)	
 
Repeat LFT within 48 hours
 
If elevation persists, establish causality
 
Complete liver CRF
 
	Investigator discretion Monitor LFT within 1 to 4 weeks or at next visit
TBL (isolated)		
> 2 × ULN (in the absence of known Gilbert syndrome)	
 
Repeat LFT within 48 hours
 
If elevation persists, discontinue the study drug immediately
 
Hospitalize if clinically appropriate
 
Establish causality
 
Complete liver CRF
 
	ALT, AST, TBL, Alb, PT/INR, ALP and γGT until resolution c (frequency at investigator discretion) Test for hemolysis (e.g., reticulocytes, haptoglobin, unconjugated [indirect] bilirubin)
> 1.5 to ≤ 2 × ULN (patient is asymptomatic)	
 
Repeat LFT within the next week
 
If elevation is confirmed, initiate close observation of the patient
 
	Investigator discretion Monitor LFT within 1 to 4 weeks or at next visit
Jaundice	
 
Discontinue the study treatment immediately
 
Hospitalize the patient
 
Establish causality
 
Complete liver CRF
 
	ALT, AST, TBL, Alb, PT/INR, ALP and γGT until resolution c (frequency at investigator discretion)
Any AE potentially indicative of a liver toxicity*	
 
Consider study treatment interruption or discontinuation
 
Hospitalization if clinically appropriate
 
Establish causality
 
Complete liver CRF
 
	Investigator discretion

aElevated ALT/AST > 3 × ULN and TBL > 2 × ULN but without notable increase in ALP to > 2 × ULN

b(General) malaise, fatigue, abdominal pain, nausea, or vomiting, or rash with eosinophilia

cResolution is defined as an outcome of one of the following: (1) return to baseline values, (2) stable values at three subsequent monitoring visits at least 2 weeks apart, (3) remain at elevated level after a maximum of 6 months, (4) liver transplantation, and (5) death.

Alb=albumin, AESI=adverse event of special interest, ALP=alkaline phosphatase, CRF=case report form, INR=international normalized ratio, γGT=gamma glutamyl transferase, LFT=liver function test, PT=prothrombin time, TBL=total bilirubin, ULN= upper limit normal

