### **5.6.2 Discontinuation of study treatment**

Discontinuation of study treatment for a patient occurs when study treatment is stopped earlier than the protocol planned duration, and can be initiated by either the patient or the investigator. If discontinuation occurs for any reason in a treatment period (i.e. Treatment Period 1 or 2), the investigator/qualified site staff must make every effort to determine the primary reason for the patient's discontinuation from the study. This information will then be recorded by the investigator/qualified site staff in the applicable eCRF section.

Study treatment must be discontinued if the investigator determines that continuation of study treatment would result in a significant safety risk for a patient.

The following circumstances require study treatment discontinuation:

- Withdrawal of informed consent
- Emergence of the following AEs:
  - a. Any severe AE or SAE that is not compatible with administration of study medication, including AEs that require treatment with prohibited co-medication
  - b. Onset of lymphoproliferative disease or any malignancy except for treated basal cell carcinoma, treated actinic keratoses, treated *in situ* carcinoma of the cervix or non-invasive malignant colon polyps, which are being or have been removed

- c. Life-threatening infection
- d. Severe hypersensitivity reaction or anaphylactic reaction
- e. Any laboratory abnormalities that in the judgment of the investigator are clinically significant and are deemed to place the patient at a safety risk for continuation in the study (general guidance on clinically notable laboratory values is provided in [Appendix 1](#))
- f. Pregnancy
- g. Use of any biologic immunomodulating agent except secukinumab

For patients who discontinue study treatment the CRF should be completed, giving the date and primary reason for stopping study treatment.

The investigator must also contact the IRT to register the patient's discontinuation from study treatment.

If study drug discontinuation occurs because the treatment code has been broken, please refer to Section [5.5.9](#).

Efficacy and safety will be assessed in detail at every study visit, and patients who are deemed not to be benefiting from the study treatment based upon safety and efficacy assessments by the investigator or for any reason on their own accord will be free to discontinue participation in the study at any time.

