### **7.3 Liver safety monitoring**

To ensure patient safety and enhance reliability in determining the hepatotoxic potential of an investigational drug, a standardized process for identification, monitoring and evaluation of liver events has to be followed.

The following 2 categories of abnormalities / AEs have to be considered during the course of the study (irrespective of whether classified/reported as (S)AE):

- Liver laboratory triggers, which will require repeated assessments of the abnormal laboratory parameter

- Liver events, which will require close observation, follow-up monitoring and completion of the standard base Liver CRF pages

Every liver laboratory trigger or liver event should be followed up by the investigator or designated personnel at the trial site as summarized below (please see [Appendix 2](#) for detailed information).

For the liver laboratory trigger:

- Repeating the liver function test (LFT) within the next week to confirm elevation.

These LFT repeats must be performed using the central laboratory if possible. If this is not possible, then the repeats can be performed at a local laboratory to monitor the safety of the patient. Repeats laboratory must then be performed at central laboratory as soon as possible. If a liver event is subsequently reported, any local LFTs previously conducted that are associated with this event must be reported on the Liver CRF pages.

- If the elevation is confirmed, close observation of the patient will be initiated, including consideration of treatment interruption if deemed appropriate.

For the liver events:

- Repeating the LFT to confirm elevation as appropriate
- Discontinuation of the investigational drug if appropriate
- Hospitalization of the patient if appropriate
- A causality assessment of the liver event via exclusion of alternative causes (e.g. disease, co-medications)
- An investigation of the liver event, which needs to be followed until resolution

These investigations can include serology tests, imaging and pathology assessments, hepatologist consultancies, based on the investigator's discretion. All follow-up information, and the procedures performed must be recorded on appropriate CRF pages, including the liver event overview CRF pages.

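### Read literally, Table 13-3 sets no mandatory stop for TBL >2×ULN with ALP >2×ULN at ALT/AST >3 to 5×ULN, although TBL >2×ULN alone has one

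*Protocol*

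**What the plan says.** The liver rules are in protocol Appendix 2 (Tables 13-2 and 13-3), Section 7.3 and Section 5.6.2.

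**Table 13-3**
- Potential Hy's Law case: immediate stop. Footnote a limits it to "Elevated ALT/AST > 3 × ULN and TBL > 2 × ULN but without notable increase in ALP to > 2 × ULN".
- TBL >2×ULN, under a heading restricted to isolated bilirubin rises: repeat within 48 hours, then "If elevation persists, discontinue the study drug immediately". Known Gilbert syndrome is excepted.
- ALP >2×ULN, also restricted to isolated rises: 48-hour repeat, causality and Liver CRF; no stop.
- Asymptomatic ALT/AST >3 to 5×ULN: "Repeat LFT within the next week", then close observation if confirmed; no stop.
- ALT/AST >5 to 8×ULN: 48-hour repeat, and "If elevation persists for more than 2 weeks, discontinue the study drug".
- Immediate stop also for ALT/AST >8×ULN, for >3×ULN with INR >1.5 or with a listed symptom, and for jaundice.

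**Table 13-2** lists TBL >2×ULN ("in the absence of known Gilbert syndrome") and ALP >2×ULN (without known bone pathology) as liver events. Neither entry is restricted to isolated rises.

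**Section 7.3** requires close observation, follow-up monitoring and Liver CRF pages for liver events, with a causality assessment and an investigation carried through to resolution. Stopping the drug is left to what is appropriate. For a laboratory trigger the wording is "including consideration of treatment interruption if deemed appropriate".

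**Section 5.6.2** makes the stop depend on the investigator: "Study treatment must be discontinued if the investigator determines that continuation of study treatment would result in a significant safety risk for a patient". Among the adverse events that require a stop, item e is "Any laboratory abnormalities that in the judgment of the investigator are clinically significant and are deemed to place the patient at a safety risk".

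**The concern.** A follow-up table should not become more lenient as more liver tests become abnormal. Read as printed, this one does. Bilirubin above 2×ULN alone leads to a stop if it persists at 48 hours. Adding ALT/AST >3 to 5×ULN makes it a Hy's Law case with an immediate stop. Adding ALP >2×ULN as well takes the patient out of the Hy's Law row through footnote a, and the bilirubin is no longer isolated, so that row's stop is lost too.

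What is at stake is patient safety: whether an asymptomatic patient with a combined bilirubin, ALP and transaminase rise has a fixed stopping rule or relies on one investigator's judgment.

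**Working it through.** The plan gives no figure to reproduce. The check applies each row of Table 13-3 to defined cases and then counts doses.

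**Step 1: rows that apply.** Assume no listed symptom, no jaundice, INR ≤1.5, no known Gilbert syndrome and no known bone pathology. Values are multiples of ULN; TBL is 2.5 throughout.

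| ALT/AST | ALP 1 | ALP 2.5, heading read literally | ALP 2.5, TBL row applied to all |
|---|---|---|---|
| 1 | 48 h repeat, stop if persistent | Depends on the meaning of *isolated* | 48 h repeat, stop if persistent |
| 4 | Immediate stop (Hy's Law) | Repeat within a week, observe; no stop | 48 h repeat, stop if persistent |
| 6 | Immediate stop (Hy's Law) | 48 h repeat, stop after >2 weeks | 48 h repeat, stop if persistent |
| 9 | Immediate stop | Immediate stop | Immediate stop |

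In the first row, if *isolated* means that no other liver test is raised, no laboratory row applies. If it means only that ALT/AST is not raised, the TBL row applies and there is no gap. The table does not define the word.

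**Step 2: doses after the finding, ALT/AST >3 to 5.** Table 6-1 schedules post-baseline chemistry at Weeks 4, 8, 12 and 24. Doses after Week 4 are at Weeks 8, 12, 16 and 20 (Table 6-2). Assume the same-day dose is given before the central laboratory result arrives.

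- Week 4 sample: Weeks 8, 12, 16, 20 = 4 doses left
- Week 8 sample: Weeks 12, 16, 20 = 3
- Week 12 sample: Weeks 16, 20 = 2
- Week 24 sample: 0

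A finding at Week 4, 8 or 12 therefore leaves 2 to 4 doses without a fixed stop. Under the TBL-alone rule the count is 0 if the rise persists at 48 hours. The 2 to 4 is a worst case: reaching the last dose requires the pattern to last 20 − 12 = 8 to 20 − 4 = 16 weeks with no other stop row met and no stop by the investigator.

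**Step 3: ALT/AST >5 to 8.** The stop comes after more than 14 days. The next dose is nominally 28 days after the sample. With both visits at the edge of their recommended windows, the shortest gaps are:

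- Week 4 to 8: 28 − 2 − 2 = 24 days
- Week 8 to 12: 28 − 2 − 5 = 21 days
- Week 12 to 16: 28 − 5 − 5 = 18 days

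All exceed 14 days, so a stop just after two weeks normally still precedes the next dose. The rule is later here, but no extra dose is expected.

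**Step 4: how many patients.** The documents give no frequency for this pattern. Fatigue is a listed symptom (footnote b), and Section 1.1 cites a study in which 67.3% of axSpA patients had severe fatigue. If pre-existing disease fatigue counts and that figure applies here (both assumptions), at most 100 − 67.3 = 32.7% of cases with this pattern stay uncovered. If only new symptoms count, up to 100% do. The range is too wide to size the problem; it shows that the symptom row cannot be relied on to close the gap.

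**The case against.** **The bilirubin row may apply anyway.** Table 13-2 makes TBL >2×ULN a liver event with no restriction to isolated rises, and Table 13-3 is the follow-up for those events. A site could take *isolated* to mean not part of a Hy's Law case and apply the 48-hour repeat and stop. This stands as a possible reading, so the gap belongs to the literal wording. It does not settle the matter: the restriction is printed above the row, and two sites could act differently in good faith.

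**Other requirements remain.** A reader might infer that this patient gets nothing beyond a repeat test within a week and observation. The documents do not support that. The bilirubin and ALP values are liver events, so the Section 7.3 duties apply in full. What they lack is a fixed stop.

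**The investigator can stop.** A reader might also infer that dosing must continue. It need not. Section 5.6.2 makes the stop compulsory once the investigator judges the risk significant, and Section 5.5.5 permits interruption for safety. Both depend on that judgment.

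**Raised ALP points to obstruction.** The note to SAP Table 2.8-1 gives this reason for separating such cases from Hy's Law. It justifies the label, but not a weaker rule than for bilirubin alone. The same note says that these cases may still be severe drug-induced liver injury.

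**The pattern should be rare.** Exclusion criterion 15 uses 2×ULN as the entry limit for any single liver parameter. Section 3.7 does not list hepatotoxicity among the important risks; its only liver item is hepatitis B reactivation. This stands and limits the size of the point.

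**Conclusion.** The point holds in a limited form. Read literally, Table 13-3 gives no mandatory stop at ALT/AST >3 to 5×ULN with TBL and ALP both >2×ULN, in a patient without a listed symptom, jaundice, INR >1.5 or known Gilbert syndrome. Bilirubin >2×ULN alone has one, and nothing in the documents explains that ordering.

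A reader might infer a gap across the whole ALT/AST range, or 2 to 4 extra doses as the expected result. Neither follows. Only the >3 to 5 band has a dosing consequence. At >5 to 8 the stop is later but normally precedes the next dose, at >8 it is immediate, and at ≤3 the answer turns on an undefined word. The 2 to 4 doses are the worst case. Few patients are likely to be affected, which is a judgment because no frequency is given. No efficacy analysis changes. The conclusion rests on taking the restriction in the bilirubin heading at face value.

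**What to change.** In Table 13-3, delete the word *isolated* for the TBL >2×ULN row, or state that the row applies whatever the ALT/AST and ALP values. Keep the Gilbert exception. Add one sentence saying that where several rows apply, the strictest governs. A combined rise then gets at least a 48-hour repeat and an immediate stop if it persists.

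This is a wording change in one appendix table, with no added patients or scheduled visits. The downside is an earlier repeat liver test and a possible treatment stop in the few patients with this pattern, some of whom may prove to have an obstructive cause.

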### 13.3 Appendix 3: Specific renal alert criteria and actions

**Table 13-4 Specific renal alert criteria and actions**

Serum event	
Serum creatinine increase 25 – 49% compared to baseline	Confirm 25% increase after 24-48h Follow up within 2-5 days
Acute Kidney Injury: serum creatinine increase ≥ 50% compared to baseline	Follow up within 24-48h if possible Consider study treatment interruption Consider patient hospitalization /specialized treatment
Urine event	
New dipstick proteinuria ≥1+ Albumin- or Protein-creatinine ratio increase ≥ 2-fold Albumin-creatinine ratio (ACR) ≥30 mg/g or ≥ 3 mg/mmol; Protein-creatinine ratio (PCR )≥150 mg/g or >15 mg/mmol	Confirm value after 24-48h Perform urine microscopy Consider study treatment interruption / or discontinuation
New dipstick glycosuria ≥ 1+ not due to diabetes	Blood glucose (fasting) Perform serum creatinine, ACR
New dipstick hematuria ≥ 1+ not due to trauma	Urine sediment microscopy Perform serum creatinine, ACR
For all renal events:	

Document contributing factors in the CRF: co-medication, other co-morbid conditions, and additional diagnostic procedures performed
 
Monitor patient regularly (frequency at investigator’s discretion) until either:
 
Event resolution: serum creatinine within 10% of baseline or protein-creatinine ratio within 50% of baseline, or
 
Event stabilization: serum creatinine level with ± 10% variability over last 6 months or protein-creatinine ratio stabilization at a new level with ± 50% variability over last 6 months.
	

### **13.4 Appendix 4: Assessment of spondyloarthritis international society criteria for axial spondyloarthritis**

ASAS criteria for classification of axSpA will be applied as defined by [Sieper et al \(2009\)](#).

#### **Diagnosis of axial spondyloarthritis according to the assessment of spondyloarthritis international society classification criteria**

Diagnosis of axSpA (either AS or nr-axSpA) according to ASAS axSpA classification criteria to be applied in patients with back pain for at least 3 months and age of onset < 45 years:

- Sacroiliitis on imaging with  $\geq 1$  SpA feature **or**
- HLA-B27 positive with  $\geq 2$  SpA features

#### **Sacroiliitis on imaging**

- Active (acute) inflammation on MRI highly suggestive of sacroiliitis associated with SpA (see [Appendix 6](#))
- Definite radiographic sacroiliitis according to the modified New York diagnostic criteria ([van der Linden et al 1984](#)) (see [Appendix 5](#))

#### **Spondyloarthritis features**

- IBP
- Arthritis
- Enthesitis (heel)
- Uveitis
- Dactylitis
- Psoriasis
- Crohn's disease or colitis
- Good response to NSAIDs
- Family history for SpA
- HLA-B27
- Elevated C-Reactive Protein

